Feasibility Study to Improve Atrial Fibrillation Outcomes Using a Digital Application for Cardiovascular Risk Reduction: Precursor to a Multicenter Randomized Trial

Study Protocol and Statistical Analysis Plan

NCT04050982

May 17, 2022

Title Feasibility Study to Improve Atrial Fibrillation Outcomes using a Digital Application for Cardiovascular Risk Reduction: Precursor to a Multicenter Randomized Trial

Purpose

An effective intervention to support cardiovascular risk factor (CVRF) reduction in individuals with AF that can be easily provided with existing resources does not exist, despite the evidence that even though CVRF reduction has been shown to decrease AF symptom severity and burden. The digital application, AF CARE, has been specifically designed to fill this critical need to support CVRF reduction in individuals with AF, and can be easily incorporated into the care delivered to individuals undergoing AF catheter ablation (CA), but its feasibility is unknown. Demonstrating that an available digital application can improve AF outcomes would be significantly impactful.

The specific aims of this study are to: 1). Test the feasibility of AF CARE in terms of acceptability, demand, usage, adherence, and integration (1), and 2). Determine the efficacy of AF CARE based on the pre-post assessment of CVRF (LS7 and/or blood tests), AF knowledge, AF Symptom Severity and Burden (AFSS), and QOL assessment at baseline, 3, and 6 months in the AF CARE group compared to the usual care (UC) group to provide estimates of effect size.

Background and Significance

Atrial fibrillation (AF) is the most common cardiac arrhythmia disorder in the United States, contributing to a five-time greater risk of stroke and is independently associated with increased mortality (2,3). Predictions of doubling the AF population is based on aging and increased prevalence of cardiovascular risk factors (4). A predicted lifetime risk of AF rises from 20% to 33% with the addition of a single elevated CVRF (4,5,6). Innovative interventions that promote the reduction of CVRF are needed to decrease AF symptom severity and burden.

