Current AF treatment guidelines include CVRF reduction, and when reduced in a randomized group, particularly weight loss, there was a significant reduction in AF burden and AF symptoms compared to those who received usual care (7,8). A maintained weight loss of at least 10% contributed to the greatest reduction in AF symptoms and AF burden (9). While AF CA procedures significantly reduce AF symptom burden (10) and decrease AF associated mortality and morbidity (11), recurrences resulting in increased morbidity and mortality persist (12). Altering the disease substrate with CVRF reduction and modifying the electrical substrate with CA procedures has shown an improvement in post-AF ablation outcomes, with less AF symptom severity/burden (13,14).

Lifestyle modifications to reduce CVRFs are difficult. There is no consensus on which intervention for CVRF reduction is most effective (15), nor what delivery mode is most acceptable. The American Heart Association (AHA) Center for Health Technology and Innovation collaborated with the Stanford Center for Digital Health and PatientBond, a digital technology software company, to design a personalized digital application (app) that can be accessed via a smartphone, iPad, or personal computer (16). This digital app, AF CARE, delivers patient-specific messages to promote behaviors that will reduce

CVRF and improve AF knowledge, based on each individual's responses to 12 psychographic questions, 12 AHA Life's Simple 7 (LS7) questions, and specific biometrics. To date, the utility and effectiveness of AF CARE to reduce CVRF has not been tested.

Research Design

Phase I will be completed prior to randomization on 10 individuals with AF who will be asked to participate in interface testing of the digital platform for 1-3 months to identify potential programming modifications to enhance usage and adherence.

Then, the primary aim of Phase II of this study will be to determine feasibility of utilizing AF CARE to provide lifestyle modification support to patients with AF. The secondary outcome will be to compare the CVRF, AF knowledge, AF Symptom Severity and Burden, and QOL between and within the UC group and the CARE AF group. This feasibility study will use a prospective, RCT wait list design to allow for the determination of effect sizes to inform the power calculation for a multi-center trial, if found to be effective. (Phase I).

a. Sample: Sixty patients undergoing treatment for AF at Stanford Health Care.

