Inclusion: ≥ 18 years old, $\text{BMI} \geq 28 \text{ kg/m}^2$ AND one additional CVRF, access and willingness to engage in digital technology, has a valid email address and a cell phone number, and able to ambulate and speak/read English

Exclusion: Class III/IV heart failure, MI or cardiac surgery in prior 3 months, severe renal/hepatic disease, active malignancy, current/recent (within 6 months) enrollment in weight loss program.

b. Participants will be recruited when they are being followed for the management of their atrial fibrillation in the Stanford clinic.

c. Procedure: Individuals meeting inclusion criteria, but not excluded, will be invited to participate. Once consented, demographics, biometrics and baseline measures will be collected. Both groups will be asked to enter initial responses into AF CARE and then will be randomized to either the digital platform AF CARE group and UC or Wait List Group. The UC wait list group will receive usual care for the first 3 months and then they will receive the digital platform (AF CARE) after 3 months of enrollment. Both groups will be appropriately referred for smoking cessation, behavioral medicine, endocrinology, and/or sleep clinic during initial and Month 3 visit, based on screening completed at that visit. Initial measures will be collected, and repeated at Month 3, Month 6, and Month 12.

Both AF CARE/UC and Wait List Groups	Initial	Month 3 (CA)	Month 6	Month 12
Medical History and Physical	X	X	X	X
Demographics	X			
Psychographic score	X			
AHA Life's Simple 7	X	X	X	X
Biometrics- pt reported (BP, HR, RR, waist, BMI)	X	X	X	X
Blood testing, if available: Lipid panel, Blood Sugar	X		X	X
6 Minute Walk Test	X	X	X	X
Jessa AF Knowledge Questionnaire	X	X	X	X
AF Symptom Severity Scale (AFSS)	X	X	X	X

Ambulatory Monitor (Zio patch)- if available	X	X	X	X
AF Effect on Quality of Life (AFEQT)	X	X	X	X
AF CARE Group -Access to AF CARE	X-----→			
Wait List Access to AF CARE	X-----→			

AF CARE GROUP: Patients will receive personalized messages twice weekly that will include behavior recommendations for CVRF reduction and AF education from the AHA library. Messages will be patient-specific based on the initially entered psychographic profile and data entered.

Ongoing messages will include participant response requests and future messages elicited by AF CARE will be based on entered responses.

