During the protocol, 3 participant non-responses to communications will result in a message being sent to the research team to prompt a call to the participant to enforce the importance of the messaging. In addition, a participant posting a negative response (e.g. "I do not know how to get my medicine refilled") will also result in a message being sent to the research team to determine if clinical follow-up is required.

Wait List UC Group/AF CARE Group: Participants will be given a weight loss goal of 10% and other recommendations for CVRF reduction based on their initial LS7 assessment. They will be provided written educational materials to review independently on AF and AF CA treatment.

Participants in this group will receive personalized messages twice weekly that will include behavior recommendations for CVRF reduction and AF education from the AHA library starting at 3 months following randomization. Measurable Outcomes: (See Table above).

- a. CVRF will be evaluated using the pre-post measures of the AHA Life's Simple 7, along with patient reported blood pressure, BMI, blood tests (lipids and glucose), and 6-minute walk test.
- b. AF knowledge will be evaluated with the Jessa AF Knowledge Questionnaire
- c. AF Symptom Severity and Burden will be measured with the AF Symptom Severity Scale
- d. QOL will be measured with the AF Effect on Quality of Life Questionnaire, and the Patient Health Questionnaire-9

Data Analysis: Demographic data will be analyzed using descriptive statistics for continuous data and frequencies and percentages for categorical data.

The feasibility of AF CARE will be determined by calculating acceptability, demand, AF CARE usage, adherence, and qualitative interview data analysis.

Efficacy will be evaluated on CVRF, AF Knowledge, AF symptom severity and burden, and QOL using matched pair t-tests at baseline, 3 and 6, and 15 months to determine the differences between and within groups. This data will be used to calculate the sample size required in a future multicenter trial designed to achieve 80% power to detect a change of 10% from baseline.

- d. Potential Pitfalls: Data integrity is an issue for self-reported measures in the usual care group. The level of usage with the AF CARE plan may be suboptimal or AF CARE may be ineffective in meeting study aims.

e. Sustainability: Sustainability will be determined by participant engagement and efficacy.

References

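### The only efficacy test named is the matched-pair t-test, so the comparison between the two unpaired randomised arms has no defined test

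*Combined protocol and SAP*

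**What the plan says.** The combined protocol and SAP has one sentence on efficacy analysis, in the Data Analysis paragraph. It covers cardiovascular risk factors, AF knowledge, AF symptom severity and burden, and quality of life, all to be evaluated "using matched pair t-tests at baseline, 3 and 6, and 15 months to determine the differences between and within groups".

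Two other places require a comparison of the arms. Specific aim 2 (Purpose) calls for assessment "in the AF CARE group compared to the usual care (UC) group to provide estimates of effect size". Research Design states the secondary outcome as "to compare the CVRF, AF knowledge, AF Symptom Severity and Burden, and QOL between and within the UC group and the CARE AF group".

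Under Research Design, c. Procedure, participants give baseline data and "then will be randomized to either the digital platform AF CARE group and UC or Wait List Group". The wait list has usual care for 3 months and then receives AF CARE. Neither that section nor any other describes matched pairs, paired allocation or an allocation ratio. The remaining analysis text covers only demographics and the feasibility measures.

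**The concern.** A matched-pair t-test needs two linked observations per unit. A participant's baseline and Month 3 values are linked in this way. A participant in one arm and a different participant in the other arm are not. The plan nevertheless assigns the paired test to both kinds of difference.

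Two readings are possible, and each leaves a gap:

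- **Literal.** Participants are paired across arms. The plan gives no pairing rule, and the test cannot use everyone unless the arms are the same size.
- **Charitable.** The phrase means repeated visits by the same person. Then no between-arm test is named at all.

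At stake is the between-arm effect estimate, with its interval, that Aim 2 exists to supply for a multicentre trial. Two analysts working from the same data could report different p-values and intervals. Under the charitable reading, a foreseeable fallback is to note that one arm changed significantly and the other did not, which is not a comparison of the arms.

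**Working it through.** The plan states no power, alpha, SD, dropout rate or allocation ratio for this study, and the sample of 60 has no derivation, so there is no figure of the plan's own to reproduce. **Assumptions for all that follow:** 30 per arm (60 split 1:1), two-sided 5% level, normal data, SD 1 in each arm.

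**1. Equal arms: how far the result depends on the pairing**

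Let d be the observed mean difference in SD units and r the accidental correlation created by a given pairing.

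- Independent groups: SE = √(2/30) = 0.258. At d = 0.5, t = 0.5/0.258 = 1.94 on 58 df, p = 0.058. The 95% CI half-width is 2.002 × 0.258 = 0.52.
- Paired: SE = 0.258 × √(1 − r), on 29 df, with critical value 2.045. The mean difference is still 0.5 for every pairing; only the SE moves.
- Under random pairing, r has mean 0 and SD 1/√29 = 0.186, so its central 95% is about ±0.364.

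| r | Paired t | p | CI half-width (SD) |
|---|---|---|---|
| +0.364 | 0.5/(0.258 × √0.636) = 2.43 | 0.022 | 0.42 |
| 0 | 1.94 | 0.063 | 0.53 |
| −0.364 | 0.5/(0.258 × √1.364) = 1.66 | 0.108 | 0.62 |

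For p < 0.05, r must exceed 1 − [0.5/(0.258 × 2.045)]² = 0.10. The chance of that is P(Z > 0.1035/0.186) = 0.29. Simulation agrees: over 200 datasets with 5,000 random pairings each, the central 95% of p was 0.022 to 0.108, and 29% of pairings fell below 0.05.

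**2. Unequal arms: participants who cannot be paired**

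With independent dropout from 30 per arm, P(unequal) = 1 − Σ P(k)², where P(k) is the binomial probability of k completers. The variance ratio is (2/min)/(1/n₁ + 1/n₂).

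| Scenario | P(arms unequal) | Mean number unpaired | Mean variance ratio |
|---|---|---|---|
| 10% dropout | 0.83 | 1.8 | 1.03 |
| 20% dropout | 0.87 | 2.5 | 1.05 |
| Simple 1:1 randomisation of 60, no dropout | 1 − 0.103 = 0.90 | 60 × 0.103 = 6.2 | not computed |

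**3. Average behaviour under random pairing**

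In 200,000 simulated trials, type I error was 5.0% for both tests. Power at d = 0.5 was 46.4% paired and 47.6% independent. The average loss is therefore small.

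**4. Charitable reading: comparing significance across arms**

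If w is the power of the within-arm paired test at n = 30, two arms with the same true change disagree with probability 2w(1 − w). For a change of 0.2 SD, w = 0.185 and this is 2 × 0.185 × 0.815 = 0.30. For 0.4 SD, w = 0.563 and it is 0.49. For 0.5 SD, w = 0.754 and it is 0.37.

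**5. Precision of valid alternatives**

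Half-widths in SD units, where ρ is the baseline-to-follow-up correlation:

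| Method | Formula | ρ = 0.5 | ρ = 0.7 |
|---|---|---|---|
| Two-sample test of change | 0.517 × √(2(1 − ρ)) | 0.52 | 0.40 |
| ANCOVA (57 df) | 2.002 × 0.258 × √(1 − ρ²) | 0.45 | 0.37 |

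**The case against.** The strongest reply is that nobody intends to pair strangers. Aim 2 speaks of pre-post assessment, so matched pairs most naturally means repeated visits by one person. On that reading the re-pairing and discarded-completer figures do not apply and the defect is one omitted test name. This is fair as to the likely intention, but Aim 2 still requires a between-arm comparison and the plan still names no test for it.

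Second, the 29% is taken where p sits close to 0.05. That is right. One simulated dataset at each value of d gave the share of random pairings that reversed the verdict: 0% at 0.3, 0.9% at 0.4, 7% at 0.45, 29% at 0.5, 33% at 0.55, 6% at 0.6 and 0% at 0.7. The verdict is fragile only in a narrow band, and the plan attaches no decision to p < 0.05. The interval width, however, varies with the pairing at every d. Deliberate pairing in sorted order can manufacture significance (p = 0.018 against 0.44 at d = 0.2), but that would be manipulation, and the case does not rest on it.

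Third, feasibility is the primary aim, and the arm means and SDs used to size the next trial do not depend on pairing. This stands and limits the severity.

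Fourth, the remedy reaches beyond the missing test. Partly so: the essential correction is an independent-groups comparison, and ANCOVA and the sample-size wording are improvements added to it. Restricting the usual-care contrast to Month 3 is not optional in the same sense, because after that visit the wait list also receives AF CARE.

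**Conclusion.** The concern holds. As written, the stated test is wrong for the between-arm comparison, and under either reading Aim 2 and the secondary outcome have no defined between-arm analysis.

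The problem is undefined inference rather than bias. In the borderline case (30 v 30, observed d = 0.5), arbitrary pairing moves p between about 0.02 and 0.11 and the CI half-width between 0.42 and 0.62 SD. With 10–20% dropout the arms end unequal in 83–87% of trials. These sizes rest on the assumed 1:1 split, SD and dropout; the absence of a valid between-arm test rests on the text alone. It should be fixed, but it does not threaten the primary feasibility aim.

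**What to change.** Replace the efficacy sentence with wording to this effect:

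- Between-group effects are estimated at Month 3, before the wait list receives AF CARE, by ANCOVA of the Month 3 value on randomised arm and baseline value. The analysis uses all participants with a Month 3 value, in the arm to which they were randomised, and reports an adjusted mean difference with 95% CI. A two-sample test of change would also be valid but is less precise.
- Paired t-tests describe within-arm change only.
- Arm contrasts after Month 3 are descriptive, as earlier versus delayed AF CARE. Aim 2's reference to a 6-month comparison with usual care should be aligned with this.
- Two sets of outcomes need a note. The schedule row "Blood testing, if available: Lipid panel, Blood Sugar" has no Month 3 entry. The plan also says "QOL will be measured with the AF Effect on Quality of Life Questionnaire, and the Patient Health Questionnaire-9", but the second instrument is not in the schedule. Outcomes without a Month 3 value have only the descriptive later contrasts.

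The same edit should settle how this study feeds the next, which is to be "designed to achieve 80% power to detect a change of 10% from baseline". That target reads as within-person change and should be stated as a between-arm difference. The sample size should use the pooled within-arm SD of the follow-up value and the baseline-to-follow-up correlation. The observed difference should serve only as a plausibility check: at 30 per arm an observed d of 0.5 has a 95% CI of 0.5 ± 0.52, or −0.02 to 1.02, whereas the SD is known to within about −15% to +22% (58 df).

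The efficacy sentence also lists 15 months while the schedule ends at Month 12; these should be reconciled in the same revision.

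The cost is one paragraph of analysis text, a matching edit to Aim 2 and a few lines of code. No blood draw or questionnaire is added.

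### Within-group symptom and quality-of-life changes that span Month 3 can mix catheter ablation with the AF CARE app, and the plan does not say which contrast will size the next trial

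*Combined protocol and SAP*

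**What the plan says.** All references are to the combined protocol and SAP.

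- **Ablation in the setting.** The Purpose describes the app as fitting into "care delivered to individuals undergoing AF catheter ablation (CA", where the abbreviation stands for catheter ablation.
- **Ablation in the schedule.** The table under Research Design, c. Procedure is headed "Both AF CARE/UC and Wait List Groups", and its Month 3 column carries CA in parentheses. No other text schedules ablation. It is not an inclusion criterion, and recruitment is from a clinic that manages AF in general.
- **The wait-list switch.** The Procedure says of the wait-list arm that "they will receive the digital platform (AF CARE) after 3 months of enrollment". The paragraph on that group repeats the timing: "starting at 3 months following randomization".
- **What ablation does.** Background and Significance states: "While AF CA procedures significantly reduce AF symptom burden (10" (the number is a citation). It also credits ablation with lower AF-associated mortality and morbidity. It states no effect on Life's Simple 7 (LS7), BMI, lipids or AF knowledge.
- **The analysis.** Data Analysis evaluates cardiovascular risk factors, AF knowledge, AF symptoms and quality of life "using matched pair t-tests at baseline, 3 and 6, and 15 months to determine the differences between and within groups". Neither Data Analysis nor Potential Pitfalls mentions ablation.
- **The use of the results.** "This data will be used to calculate the sample size required in a future multicenter trial", and that trial is "designed to achieve 80% power to detect a change of 10% from baseline". The contrast and time point to be used are not named. Aim 2 in the Purpose speaks of the AF CARE group against usual care at 3 and 6 months.

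**The concern.** AFSS is an efficacy outcome, and the plan's own background expects symptom burden to fall after ablation. If ablation happens at or near Month 3, a participant's change from before that visit to Month 6 or later contains the ablation effect as well as any app effect. In the wait-list arm the difficulty is sharper, because the app starts at the same moment. The before-and-after-app comparison in that arm is then also a before-and-after-ablation comparison for anyone ablated at that point.

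An app with little effect on symptoms could therefore show a clear within-group improvement. The study's stated reason for a randomized wait-list design is to provide effect sizes for a larger trial. If a within-group change of this kind were carried forward, that trial could be too small.

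**Working it through.** **There is no planned figure to reproduce.** The 60 participants come without a power calculation. The future trial's 80% power and 10% change come without an SD, alpha or sample size.

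**Step 1: what each contrast contains, for participants who have ablation around Month 3.** The documents do not say whether Month 3 measures come before or after it, so both cases are shown. Within-group rows also contain any time trend.

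| Contrast | Measures before CA | Measures after CA |
|---|---|---|
| AF CARE arm, baseline to Month 3 | app | app + CA |
| AF CARE arm, baseline to Month 6 | app + CA | app + CA |
| Wait list, baseline to Month 6 | app + CA | app + CA |
| Wait list, Month 3 to Month 6 | app + CA | app + any continuing CA effect |
| Between arms, change to Month 3 | app against usual care | the same; CA cancels on average |
| Between arms, change to Month 6 | 6 against 3 months of app; CA cancels on average | the same |

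Cancellation assumes that the app does not alter who has ablation.

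**Step 2: possible inflation (assumed inputs).** Let a be the app effect, c the ablation effect and p the share of participants ablated, with effects in SD units and SD set to 1. The within-group change is

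d = a + p × c.

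For a two-arm trial with 1:1 allocation, two-sided alpha 0.05 and 80% power (only the 80% is from the plan):

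- n per arm = 2 × (1.960 + 0.842)² / d² = 15.70 / d², rounded up
- power for the true effect = Φ(a × √(n/2) − 1.960)

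With a = 0.3, the correct n is 15.70 / 0.09 = 174.4, so 175 per arm.

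| c | p | d | n per arm | Power for a = 0.3 |
|---|---|---|---|---|
| any | 0 | 0.300 | 175 | 80% |
| 0 | any | 0.300 | 175 | 80% |
| 0.3 | 0.25 | 0.375 | 112 | 61% |
| 0.5 | 0.50 | 0.550 | 52 | 33% |
| 0.8 | 1.00 | 1.100 | 13 | 12% |

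Over a = 0.2 to 0.5, c = 0.3 to 0.8 and p = 0.25 to 1, inflation runs from 15% (0.5 to 0.575) to 400% (0.2 to 1.0). Power for the true app effect then runs from 69% down to 8%.

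**Step 3: the Month 6 between-arm difference.** With equal ablation rates it is (a6 + p × c) − (a3 + p × c) = a6 − a3, where a3 and a6 are the effects after 3 and 6 months of app use. With a3 = 0.3 and a6 = 0.3 to 0.5, it is 0.0 to 0.2 SD. That is diluted, not inflated.

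**Step 4: precision of the Month 3 between-arm difference.** With an assumed 30 per arm, the 95% CI half-width is 1.960 × √(2/30) = 0.51 SD.

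**The case against.** The strongest reply is that one parenthetical label carries much of the weight. Ablation is not required for entry, and the sample is people treated for AF generally. A reader might infer that every participant has ablation at Month 3 and that every later within-group result is contaminated. The documents do not support this. Uptake is unstated and could be low or zero. The claimed benefit concerns symptom burden, morbidity and mortality, not the risk factors and knowledge that the app targets. This stands, and it limits the point to participants who have ablation and to AFSS, plausibly AFEQT.

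A reader might also infer that the next trial will be undersized. That is conditional too. Aim 2 points to a comparison with usual care, where ablation tends to cancel. Data Analysis sets a fixed target of a 10% change. If that target is used, the pilot supplies only the variability, and mixed ablation receipt pushes the sample size the other way. It adds p(1 − p)c² to the variance: with p = 0.5 and c = 0.8 that is 0.25 × 0.64 = 0.16, so n rises by 16% when the SD without ablation is 1. This stands as well.

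The schedule has a medical history and physical at every visit, so ablation could be captured there. But the plan does not say that it will be, or that it will be used in the analysis.

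What the reply does not remove is this: within-group tests across Month 3 are named as efficacy analyses, nothing separates ablation from the app, and the contrast that will size the next trial is left open.

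**Conclusion.** The point holds in limited form. Where participants have ablation around Month 3, within-group changes in AFSS, and plausibly AFEQT, that span that visit cannot be attributed to AF CARE. If they are used to size the next trial, the app effect can be overstated.

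The amount cannot be determined from the documents. The illustrations give anything from no inflation (zero uptake, or an outcome that ablation does not move) to a severe loss of power. They rest on assumed effects, uptake, alpha and allocation, on a common SD of 1, and on no time trend. The Month 6 between-arm contrast avoids most of the ablation problem but not the switch of the wait-list arm to the app.

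This should be fixed. It concerns secondary efficacy estimates, and the primary feasibility aim is unaffected.

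**What to change.** 1. **Clarify and record.** Reconcile the CA label in the schedule with the eligibility and recruitment text. State whether Month 3 measures are taken before or after ablation. Record receipt and date of ablation for every participant. The clinical timing of ablation stays as it is.
2. **Name the source of the effect size.** Use the randomized between-arm difference in baseline-to-Month 3 change, by a two-sample test or ANCOVA adjusted for baseline, for both the effect size and the SD. Flag participants whose ablation preceded their Month 3 measures. Keep them in the main comparison, since ablation occurs after randomization, and show the result without them as a sensitivity analysis. As the table reads, blood tests are not scheduled at Month 3, so this contrast is not available for them.
3. **Relabel the rest.** Report within-group AFSS and AFEQT changes that span Month 3 descriptively, by arm and ablation status. Do not present them as AF CARE efficacy or use them as sample-size input.

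The cost is one data field and some analysis wording, with no added participants, visits or procedures. The price is that later within-group results become descriptive, and that the Month 3 estimate is imprecise (about ±0.5 SD with an assumed 30 per arm). The future sample size should therefore be shown over a range of effects.

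### Efficacy rests only on complete-pair t-tests, with no as-assigned analysis set and no statement that people who stop using AF CARE are still measured; the effect sizes may be biased, in a direction the documents do not fix

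*Combined protocol and SAP*

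**What the plan says.** **Method.** Under Data Analysis, efficacy is assessed "using matched pair t-tests at baseline, 3 and 6, and 15 months to determine the differences between and within groups". No other efficacy method is named.

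**Design.** The sample is "Sixty patients undergoing treatment for AF at Stanford Health Care", who "will be randomized to either the digital platform AF CARE group and UC or Wait List Group". The allocation ratio is not stated. The wait-list group has usual care first and "then they will receive the digital platform (AF CARE) after 3 months of enrollment", so Month 3 is the only visit that compares AF CARE with usual care alone.

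**Follow-up.** The Procedure section says "Initial measures will be collected, and repeated at Month 3, Month 6, and Month 12". The visit table covers both groups and sets no condition on app use.

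**Disengagement.** Potential Pitfalls concedes that "The level of usage with the AF CARE plan may be suboptimal". In the AF CARE group description, "3 participant non-responses to communications will result in a message being sent to the research team to prompt a call to the participant". The stated purpose of that call is to stress the importance of the messages, not to obtain outcome data.

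**Use of the result.** "This data will be used to calculate the sample size required in a future multicenter trial designed to achieve 80% power".

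**Not stated anywhere.** An analysis population, a missing-data method, an expected loss to follow-up, a sensitivity analysis, or whether someone who stops using the app is still measured.

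**The concern.** A paired t-test needs both values of each pair. Someone without a Month 3 value leaves the Month 3 test; someone without a Month 6 value leaves the Month 6 test. The people analysed can therefore differ by visit and by outcome, and the plan has no as-assigned set to bring them back.

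Unequal loss is plausible here. Until Month 3 only the AF CARE arm receives messages twice a week with requests to reply, while wait-list participants still have the app to come. If people who tire of the messages also miss visits, and if they are the poorer responders, the AF CARE pairs that remain look better than the arm as randomised.

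What is at stake is the effect size, which is the product of Aim 2 and the input to the next trial's sample size. A confidence interval computed on complete pairs would not show this error.

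This point concerns who is in the analysis. That a paired test is not a comparison of two independent arms is a separate matter: correcting the test alone would still leave a complete-case analysis.

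**Working it through.** **Plan's own figure.** The total of 60 cannot be reproduced: no alpha, SD, effect or dropout is given for this study. The 80% power refers to the future trial.

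**Inputs.** From the documents: 60 participants, two randomised groups, visits at baseline and Months 3, 6 and 12, 80% power for the next trial. Assumed: 1:1 allocation (30 per arm), two-sided alpha 0.05, true effect 0.30 SD, and all dropout rates and correlations below.

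**1. Bias at Month 3 among complete pairs.** Let d be the share lost in an arm, c the standard normal quantile of d, φ the standard normal density, and ρ the correlation between staying in follow-up and improving. The mean change among those kept shifts by ρ·φ(c)/(1−d), in SDs of change. The bias is the AF CARE shift minus the wait-list shift.

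- d = 0.30: c = −0.524, φ = 0.348, so the shift is ρ × 0.348/0.70 = 0.497ρ.
- d = 0.10: c = −1.282, φ = 0.175, so the shift is ρ × 0.175/0.90 = 0.195ρ.

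| Loss, AF CARE / wait list | Selection (ρ) | Bias (SD) |
|---|---|---|
| any | 0 in both arms | 0 |
| equal | same in both arms | 0 |
| 30% / 10% | 0.3 to 0.5, AF CARE only | +0.15 to +0.25 |
| 30% / 10% | 0.3 to 0.5, both arms | +0.09 to +0.15 |
| 10% / 30% | 0.3 to 0.5, both arms | −0.09 to −0.15 |
| 30% / 10% | −0.3, AF CARE only (improvers stop attending) | −0.15 |

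A simpler form gives the same order: bias = share missing × gap between kept and lost, when only AF CARE has selective loss. With 20% missing and a gap of 0.5 SD, 0.20 × 0.5 = 0.10 SD.

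**2. Consequence for the next trial.** A true effect of 0.30 needs 175 per arm for 80% power.

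| Estimate carried forward | Planned per arm | Real power at 0.30 |
|---|---|---|
| 0.30 | 175 | 80% |
| 0.41 | 94 | 54% |
| 0.45 | 78 | 47% |
| 0.15 | 698 | above 99% (oversized) |

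**3. Scale against random error.** With 30 per arm the 95% half-width is 1.96 × √(2/30) = 0.51 SD. With 21 per arm it is 1.96 × √(2/21) = 0.60 SD.

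**4. How much a mixed model recovers** (large-sample simulation, visit correlation 0.6, true value 0.30).

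- Month 6, loss of 20–40% driven by the already observed Month 3 change (odds 1.6–3.8 per SD poorer): complete pairs give 0.34–0.48; a likelihood model using all observed visits gives 0.30. These are single-group changes, not arm differences. When loss depended only on the Month 3 level, the paired estimate was itself unbiased.
- Month 3, loss in AF CARE only, driven by the unseen Month 3 change, with 20% lost and odds 2.5 per SD: the paired difference is about 0.44 and a common-baseline likelihood model gives about 0.42. The model removes about 0.02–0.03 of a bias of about 0.14, roughly a fifth. The fraction is similar across 10–30% loss and odds of 1.6–3.8.

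The model works when the value that drives loss has been seen. At Month 3 a missing participant has only a baseline, so there is little to recover from.

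**The case against.** A reader might infer that nothing keeps app drop-outs in follow-up, that the effect is therefore estimated only in engaged users, and that it is biased toward AF CARE. The documents do not support that.

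- Visits are scheduled for both groups whatever the app use, and they include a physical examination and a walk test. Participants are recruited while being followed in the AF clinic. A non-user who attends Month 3 stays in the paired test, and no section withdraws or excludes non-users.
- Non-response prompts a call. It is aimed at messaging, so it lessens the risk of lost outcomes without removing it.
- Low usage is named as a possibility, not an expectation, and usage is not the same as a missing outcome.
- Direction depends on unknown behaviour. Wait-list participants might leave because access is delayed, and improved users might stop attending. The table above includes zero and negative biases.
- After Month 3 both arms have AF CARE, so the Month 6 figures cannot show a biased comparison with usual care.
- Efficacy is secondary in a feasibility study of 60, and an illustrative bias of 0.10 SD is small beside a half-width of 0.51 SD.

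All of this stands against a claim of certain or directional bias. It does not close the gap: the method still drops incomplete pairs, no as-assigned set is defined, and the point estimate is what goes forward. Larger numbers reduce random error but not selection.

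**Conclusion.** The point holds as a risk that the plan leaves uncontrolled, not as a demonstrated bias. It is certain from the text that the sole efficacy method is a complete-pair analysis, with no as-assigned set, no missing-data method and no explicit rule to measure people who stop using the app. Whether bias results, how large it is and which way it runs rest wholly on assumed dropout. In the scenarios worked, it lies between −0.15 and +0.25 SD. A direction toward AF CARE is the more plausible because only that arm receives messages before Month 3, but this is judgement and not a finding in the documents.

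It should also not be inferred that a mixed model cures the Month 3 comparison. It handles loss explained by observed visits, and in the Month 3 scenarios it removed only about a fifth of the bias. This is a cheap improvement, worth making because a better method than the stated one is readily available.

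**What to change.** 1. In Data Analysis, replace the paired t-tests with one mixed model per outcome. Include every randomised participant as assigned, use all observed scheduled visits (baseline, 3, 6 and 12) with a common baseline mean, and report the Month 3 arm difference with its 95% CI as the randomised effect estimate.
2. In Procedure, add one sentence: Month 3, 6 and 12 measures are collected whether or not the participant still uses AF CARE.
3. Add a sensitivity analysis that assumes no change from baseline for AF CARE participants with no Month 3 value, and report the number analysed per arm at each visit.

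Items 2 and 3 carry the Month 3 comparison; item 1 alone does not.

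**Cost.** Revised SAP wording, one Procedure sentence, slightly more analysis, and modest effort to reach non-users through visits and calls already planned. The effect estimate may come out smaller.
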